## 5.2 Criteria for Starting Subsequent Cycles

A cycle may be repeated every 28 days if the patient has at least stable disease and has again met laboratory parameters as defined in the eligibility section, [Section 4.0](#).

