**8.0 EVALUATIONS/MATERIAL AND DATA TO BE ACCESSIONED**

**8.1 Required Clinical, Laboratory and Disease Evaluation**

All clinical and laboratory studies to determine eligibility must be performed within 7 days prior to enrollment unless otherwise indicated. Laboratory values used to assess eligibility (see [Section 4.0](#)) must be no older than seven (7) days at the start of therapy. Laboratory tests need **not** be repeated if therapy starts **within** seven (7) days of obtaining labs to assess eligibility. If a post-enrollment lab value is outside the limits of eligibility, or laboratory values are older than 7 days, then the following laboratory evaluations must be re-checked within 48 hours prior to initiating therapy: CBC with differential, bilirubin, ALT (SGPT) and serum creatinine. If the recheck is outside the limits of eligibility, the patient may not receive protocol therapy and will be considered off protocol therapy. Imaging studies must be obtained within 14 days prior to start of protocol therapy (repeat the tumor imaging if necessary).

STUDIES TO BE OBTAINED	Pre-Study	During Cycle 1	Prior to Subsequent Cycles^
History	X	Weekly	X
Physical Exam with vital signs	X	Weekly	X
Neurologic Exam	X	Weekly	X
Pregnancy Test 	X	End of Cycle 1 	Every other cycle x 2 then q 3 cycles 
Height, weight	X	Weekly	Every other week during cycles 2 and 3 then prior to each cycle
BSA	X		X
Performance Status	X		
CBC, differential, platelets	X	Twice Weekly (every 3 to 4 days) 	Weekly 
Urinalysis	X		
Electrolytes including Ca ++ , PO 4 , Mg ++	X	Weekly	X
Creatinine, ALT, AST, bilirubin	X	Weekly	X
Albumin	X		X
Amylase, Lipase	X		X
Tumor Disease Evaluation	X	End of Cycle 1 	Every other cycle x 2 then q 3 cycles 
Patient Diary 		Weekly	X
Pharmacokinetics 	X	X	
Pharmacodynamic Studies 	X	X	
Tissue Studies  (Part C)	X		
Snellen Eye Chart 	X		Every other cycle x 2 then q 3 cycles 

^ Studies may be obtained within 72 hours prior to the start of the subsequent cycle.

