 Women of childbearing potential require a negative pregnancy test prior to starting treatment; sexually active patients must use two effective methods of birth control- including a medically accepted barrier method of contraceptive method (e.g., male or female condom). Abstinence is an acceptable method of birth control. Pregnancy testing is required prior to tumor imaging per institutional guidelines.

 If patients develop Grade 4 neutropenia then CBCs should be checked every 3 to 4 days until recovery to Grade 3

 Tumor Disease Evaluation should be obtained on the next consecutive cycle after initial documentation

THIS PROTOCOL IS FOR RESEARCH PURPOSES ONLY, SEE PAGE 1 FOR USAGE POLICY

- of either a PR or CR. Please note that for solid tumor patients, if the institutional investigator determines that the patient has progressed based on clinical or laboratory evidence, he/she may opt not to confirm this finding radiographically.
- 4 Patient diary (see [Appendix VII](#)) should be reviewed and uploaded into RAVE weekly during Cycle 1, and after completion of each treatment cycle.
  - 5 See [Section 8.3](#) for timing of PK studies.
  - 6 In consenting patients. See [Section 8.4](#) for timing of Pharmacodynamic studies.
  - 7 See [Section 8.5](#) for details of tissue studies.
  - 8 Part C: Observations are required as scheduled during protocol treatment only; *i.e.* weekly labs and observations are not required during the “surgery window” and may be held until resuming protocol therapy.
  - 9 Patients in Part C who interrupt treatment of Cycle 1 due to required resection should have scans repeated prior to resuming protocol therapy.
  - 10 Snellen eye chart should be used to assess visual acuity. If a decline in visual acuity occurs or other visual symptoms occur, the patient should be referred to an ophthalmologist for an examination.

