Accrual to Parts B and C will only open once the MTD or recommended phase 2 dose has been determined in Part A, and may open concurrently with the PK expansion described above.

A maximum of 24 patients are expected to enroll in Parts B and C combined, assuming an inevaluability rate of 20%. We anticipate that each part of the study will require 6-12 months for enrollment.

Response for Part B will be defined as either MR, PR or CR on two consecutive 2D measurements on standard imaging done 4 weeks apart (See [Section 12.6](#)). Sustained responses are very rare in this cohort of recurrent non-DIPG HGGs. We will consider the agent of sufficient interest for further evaluation in this disease category if at least one PR or CR, or at least two MRs, is observed among 10 enrolled patients. A response rate of 20% or more would be evidence of sufficient activity. If the true response rate is 20%, then the probability of observing one or more responses among 10 evaluable patients is about 89.3%. If the response rate is 5%, then the probability of observing at least one response is about 40.1%.

Clinical benefit for Part C will be evaluated separately using the criteria of no visible disease progression six months from the start of treatment. If two or more of a cohort of up to six patients are unable to resume therapy within 6 weeks after surgery, the surgical arm will be declared not feasible. If Part B has fully accrued, Part C will close to further accrual.

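### A Part B minor response needs confirmation 4 weeks apart, but no scan is ordered 4 weeks after a first minor response

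*Combined protocol and SAP*

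**What the plan says.** Section 11.1 defines response in Part B as "either MR, PR or CR on two consecutive 2D measurements on standard imaging done 4 weeks apart". It gives no qualifier such as a minimum, and no visit window. It then finds the agent of sufficient interest "if at least one PR or CR, or at least two MRs, is observed among 10 enrolled patients". So MR counts in the definition and has its own branch in the decision rule.

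The Section 8.1 table schedules tumor evaluation at baseline, at the end of Cycle 1, and then "Every other cycle x 2 then q 3 cycles". Section 5.2 fixes the cycle length: "A cycle may be repeated every 28 days". Footnote 3 to the table orders one more evaluation, at the next cycle after first documentation "of either a PR or CR. Please note that for solid tumor patients"; the footnote then turns to progression. MR is not named. Section 12.2 has a similar sentence on a confirmatory scan, but it belongs to the RECIST criteria for solid tumors, which have no MR category.

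Two other sections bear on this:

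- Section 12.7.1, to which 12.6.7 sends CNS patients for best response, states confirmation of CR and PR as a minimum of 28 days. It has no MR row.
- Section 11.2.3 counts only a centrally confirmed CR or PR as a response for the 11.1 rule and makes every other patient a non-responder. Yet the same paragraph lists MR among the responses that need central review.

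**The concern.** The decision rule uses three response categories, but the scan that would confirm a response after one cycle is ordered for only two of them. Elsewhere MR is treated as a response: central review in 8.2.1 covers it, duration of response in 12.7.2 can start from it, and it has its own row in the overall-response table of 12.6.7. Leaving it out of footnote 3 therefore looks like an oversight.

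What is at stake is how a sustained MR is classified. Suppose a patient shows MR on every scheduled scan. Applied literally to the ordered imaging, 11.1 leaves that patient unconfirmed. Applied loosely, it counts the patient, but after a longer test than a PR or CR faces. Two sites, or two analysts, could classify the same patient differently, and in a cohort of 10 one patient can turn the decision.

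**Working it through.** **1. The plan's own figures.** Section 11.1 gives the chance of at least one response among 10 evaluable patients as about 89.3% at a true rate of 20% and about 40.1% at 5%. With the exact binomial, 1 − (1 − p)^10:

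- p = 0.20: 1 − 0.80^10 = 0.8926
- p = 0.05: 1 − 0.95^10 = 0.4013

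Both reproduce. They describe at least one response of any counted kind, so they match the full rule only if no response is an MR.

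**2. Scan dates.** With 28-day cycles, the natural reading of the 8.1 table gives scans at the ends of Cycles 1, 3, 5, 8 and 11, which are weeks 4, 12, 20, 32 and 44. The gaps are 8, 8, 12 and 12 weeks. No two scheduled post-baseline scans are 4 weeks apart.

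**3. Two readings of the interval.**

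- Exactly 4 weeks: a patient whose scheduled scans show only MR has no qualifying pair.
- At least 4 weeks: MR at weeks 4 and 12, or at 12 and 20, qualifies. The MR must then last 8 weeks, or 12 weeks from week 20 on. A first PR or CR is rescanned after one cycle, about 4 weeks.

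The 72-hour window before each cycle in 8.1 moves an interval by up to 3 days either way, if no cycle is delayed. A scan triggered by PR or CR then falls 28 ± 3 = 25 to 31 days later, so a strict 28-day minimum could exclude some of these. Scheduled scans 8 weeks apart fall 56 ± 3 = 53 to 59 days apart, well above either limit.

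**4. What the two-MR branch is worth.** Let q be the PR/CR rate and m the MR rate. Then

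P(positive) = 1 − [(1 − q − m)^10 + 10m(1 − q − m)^9].

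If no MR can count, this becomes 1 − (1 − q)^10. The documents give no split between MR and PR/CR, so the MR share is an assumption, shown over a range.

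| Total response rate | MR share | With two-MR branch | Branch lost |
|---|---|---|---|
| 20% | 25% | 0.8255 | 0.8031 |
| 20% | 50% | 0.7584 | 0.6513 |
| 20% | 75% | 0.6913 | 0.4013 |
| 5% | 25% | 0.3225 | 0.3176 |
| 5% | 50% | 0.2437 | 0.2237 |
| 5% | 75% | 0.1649 | 0.1182 |

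For example, at 20% with half MR, q = m = 0.10: 0.8^10 + 10 × 0.10 × 0.8^9 = 0.1074 + 0.1342 = 0.2416, and 1 − 0.2416 = 0.7584. Without the branch, 1 − 0.9^10 = 0.6513.

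**5. The longer interval, illustrated.** The documents give no data on how long an MR lasts. Assume exponential loss with a half-life h of 8 weeks (range 4 to 16). The chance that an MR is still present after t weeks is 2^(−t/h), and for two given MRs it is that value squared.

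| Interval | One MR confirmed | Two given MRs both confirmed |
|---|---|---|
| 4 weeks | 71% (50–84%) | 50% (25–71%) |
| 8 weeks | 50% (25–71%) | 25% (6–50%) |
| 12 weeks | 35% (13–59%) | 13% (2–35%) |

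These figures show direction only. They are not the probability of a positive decision.

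**The case against.** A reader might infer that the two-MR branch can never be met, so that the number of confirmed MRs is zero. The documents do not support that, for five reasons.

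- It needs 4 weeks to mean exactly 4 weeks. The confirmation interval in 12.7.1 is a minimum, and on that reading routine scans suffice.
- Even if the interval is exact, a first PR triggers a scan about 4 weeks later. If that scan shows MR, the patient has two consecutive measurements of at least MR at the required spacing.
- Nothing prohibits an extra scan.
- The rule speaks of MRs being observed, and the MR definition in 12.6.4 has no confirmation step. The definition just before the rule implies confirmed MRs, but the rule does not repeat it.
- If every other cycle is counted from Cycle 2, scans fall at the ends of Cycles 1, 2, 4, 7 and 10, and the first gap is 4 weeks. The later gaps are still 8 to 12 weeks.

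Two more points on that side carry weight. Section 11.2.3 is the more direct obstacle, because under it even a confirmed MR is a non-responder. And 11.5 calls the response analyses descriptive and exploratory, which limits the consequences.

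The appeal to 12.7.1 does not settle the matter. Its table has no MR row, and its note limits the confirmation requirement to non-randomized trials with response as the primary endpoint; here response is a secondary aim (1.2.1, 1.2.4). So the minimum has to be written into 11.1. Reconciling 11.2.3 alone would also leave the interval unclear.

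**Conclusion.** The mismatch stands, as an ambiguity with a practical cost. On the natural reading of the schedule, no scan 4 weeks after a first MR is ordered, although 11.1 requires that spacing and gives MR its own route to a positive decision. Read literally, a patient with only MR on scheduled scans cannot be confirmed. Read as a minimum, the patient can be, but the MR has to last 8 to 12 weeks against about 4 for PR or CR.

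The most the branch can matter, at a 20% response rate, is the gap between the two columns in step 4: about 2 percentage points if a quarter of responses are MR, 11 if half are, and 29 if three-quarters are. That is the loss if no MR ever counts, which the literal reading approaches and 11.2.3 as written would produce. The loss on the minimum reading is smaller and cannot be derived from the documents. It would also go too far to call every MR lost before the next scheduled scan a false negative, since 11.1 itself stresses sustained responses. The plan's 89.3% and 40.1% are arithmetically correct and do not depend on this point.

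**What to change.** 1. In 11.1, change the interval to at least 4 weeks, so that a sustained MR on consecutive scheduled scans counts. State one minimum in days and one visit window, and use the same pair in 12.7.1. A 28-day minimum in one place and a 25-day allowance in another would recreate the problem. This costs wording only.
2. In the same amendment, reconcile 11.2.3 with the two-MR branch: either a centrally confirmed MR counts toward the 11.1 rule, or the branch is removed. Also say whether the two MRs must be confirmed. Without this, the first change does not make the branch work. This too is wording only.
3. Optionally, add MR to the trigger in footnote 3 of 8.1, limited to patients counted in the Part B rule (Part B, plus the Part A patients whom 11.1 brings into it). This puts all three categories on the same clock. The cost is one added MRI for each patient with a first MR: footnote 3 cancels no scheduled scan, so an MR at week 4 would add a week 8 scan and leave week 12 in place. Without the limit, the trigger would reach every CNS patient in the study.

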## 8.2 Radiology Studies

- 8.2.1 Central Radiology Review for Response: Patients who respond (CR, PR, or MR) to therapy or have long term stable disease (SD) ( $\geq 6$  cycles) on protocol therapy will be centrally reviewed. COG Operations Center will notify the Imaging Center of any patient requiring central review. The Imaging Center will then request that the treating institution forward the requested images for central review. The central image evaluation results will be entered into RAVE for review by the COG Operations Center and for data analysis.

The images are to be forwarded electronically to the Imaging Research Center at Children’s Hospital Los Angeles via the LifeImage.

COG institutions that are not connected via the LifeImage can send the images on hard copy film, CD ROM, USB flash drive or by FTP. Submitted imaging studies should be clearly marked with the COG patient ID, study number (ADV1414) and date and shipped to [name] at the address below:

[name], CRP  
Administrator, Imaging Research Center  
Children’s Hospital Los Angeles  
[name]  
[name]  
[contact]  
[contact]  
E-mail: [contact]

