### 11.2.3 Evaluability for Response

Any patient who is enrolled who meets eligibility criteria for Part B and receives at least one dose of selinexor will be considered evaluable for response provided: (1) the patient demonstrates progressive disease or death while on protocol therapy; or (2) the patient is observed on protocol therapy for at least one cycle and the tumor is not removed surgically prior to the time complete response or partial response is confirmed, or (3) the patient demonstrates a complete or partial response as confirmed according to protocol criteria. Patients who demonstrate a complete or partial response confirmed by central review will be considered to have experienced a response for the application of the rule given in [Section 11.1](#). All other patients will be considered non-responders. All patients considered to have a response (CR, PR, or MR) must have imaging studies reviewed centrally at the COG. Centers will be notified by the COG about requests for scans of patients with stable disease. See [Section 8.2](#) regarding image submission instructions. The central review by COG will be provided as the final reviewed assessment of response when such becomes available.

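### Part B activity rule: Sections 11.1 and 11.2.3 disagree on whether minor responses count, and the stated probabilities are not those of the rule as written

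*Combined protocol and SAP*

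**What the plan says.** Section 11.1 sets out the Part B activity rule in three steps.

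- **Definition:** "Response for Part B will be defined as either MR, PR or CR on two consecutive 2D measurements", taken 4 weeks apart.
- **Rule:** the agent is of interest "if at least one PR or CR, or at least two MRs, is observed among 10 enrolled patients".
- **Probabilities:** "If the true response rate is 20%, then the probability of observing one or more responses among 10 evaluable patients is about 89.3"%, and "If the response rate is 5%, then the probability of observing at least one response is about 40.1"%.

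Section 11.2.3 then defines response again and refers to Section 11.1 by number. Patients with a "complete or partial response confirmed by central review will be considered to have experienced a response for the application of the rule" of Section 11.1, and "All other patients will be considered non-responders". The following sentence nevertheless names MR as a response: "All patients considered to have a response (CR, PR, or MR) must have imaging studies reviewed centrally at the COG".

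**The concern.** The two sections can give opposite answers for the same data. Suppose two of ten patients have a centrally confirmed MR and none has a PR or CR. Section 11.1 calls this a positive result. Section 11.2.3, read literally, finds no responders. Section 11.1 itself describes sustained responses as very rare in this population, so a cohort whose only responses are MRs is a realistic outcome. The reading could then be chosen after the data are seen.

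The probabilities raise a second problem. Under Section 11.1 a single MR is a response, but it does not satisfy the rule, which needs two MRs or one PR/CR. The chance of at least one response is therefore not the chance of a positive result, and the plan gives no operating characteristic for the rule it wrote.

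**Working it through.** **Does the rest of the plan settle it?** No.

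- Sections 8.2.1 and 12.7.2 treat MR as a response category, and the CNS table in 12.6.7 has an MR row.
- Section 12.6.7 sends best response to 12.7.1, where Tables 1 and 3 have no MR entry.
- Footnote 3 of Section 8.1 asks for an evaluation at the next cycle after PR or CR only, although 11.1 requires a second measurement at 4 weeks for MR as well.
- Section 11.5 uses PR/CR, or more than 12 weeks without progression, for Part B clinical benefit. That is a different endpoint.

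**The plan's own figures.** With n = 10 (Section 11.1):

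- 1 − 0.80^10 = 0.893
- 1 − 0.95^10 = 0.401

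Both stated values reproduce.

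**The rule as written in 11.1.** Let r be the PR/CR rate, m the MR rate and q = 1 − r − m. The rule fails only with no response at all, or with exactly one MR and no PR/CR:

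- P(rule met, 11.1) = 1 − [q^10 + 10·m·q^9]
- P(rule met, CR/PR only) = 1 − (1 − r)^10
- P(sections disagree) = the first minus the second, which is the chance of two or more MRs with no PR/CR

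The documents do not split the 20% or 5% between PR/CR and MR. The MR share is therefore an assumption, shown over its full range.

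Example: total rate 20%, half of it MR, so r = m = 0.10 and q = 0.80.

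- q^10 = 0.1074 and 10 × 0.10 × 0.80^9 = 0.1342
- P(rule met, 11.1) = 1 − 0.2416 = 0.758
- P(rule met, CR/PR only) = 1 − 0.90^10 = 0.651
- Disagreement = 0.107

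Reading 20% and 5% as the total MR+PR+CR rate, as 11.1 defines response:

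| MR share of responses | 20%: met under 11.1 | 20%: met, CR/PR only | 20%: disagree | 5%: met under 11.1 | 5%: met, CR/PR only | 5%: disagree |
|---|---|---|---|---|---|---|
| 0% | 89.3% | 89.3% | 0% | 40.1% | 40.1% | 0% |
| 25% | 82.6% | 80.3% | 2.2% | 32.2% | 31.8% | 0.5% |
| 50% | 75.8% | 65.1% | 10.7% | 24.4% | 22.4% | 2.0% |
| 75% | 69.1% | 40.1% | 29.0% | 16.5% | 11.8% | 4.7% |
| 100% | 62.4% | 0% | 62.4% | 8.6% | 0% | 8.6% |

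The shortfall of the 11.1 columns from 89.3% and 40.1% is the single-MR term 10·m·q^9. At a 50% share it is 13.4 points (20% rate) and 15.8 points (5% rate).

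**The other reading of the rate.** Suppose 20% and 5% are PR/CR rates and a further 10% of patients have an MR (also an assumption).

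- r = 0.20, m = 0.10, q = 0.70: rule met under 11.1 in 93.1%; disagreement 93.1 − 89.3 = about 4%.
- r = 0.05, m = 0.10, q = 0.85: rule met under 11.1 in 57.2%; disagreement 57.2 − 40.1 = about 17%.

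On this reading the stated figures are too low for the rule in 11.1. On the first reading they are too high.

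**The case against.** The strongest reply is that the two sections can be reconciled. The rule in 11.1 counts PRs, CRs and MRs by name and never counts responders, so calling an MR patient a non-responder need not stop that patient being one of the two MRs. The 11.2.3 sentence could simply require central confirmation for the PR/CR limb, and sending MRs to central review makes most sense if they are used. This may well be what was intended, but the text does not compel it. Section 11.2.3 says that it is defining response for this rule, and its exclusion covers all other patients.

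Second, no stated probability is wrong, and 11.1 never says that 89.3% is the chance of meeting the rule. That stands. The point is that the figures follow the rule directly and are the only ones offered for it.

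Third, the size depends on an MR share that nobody has stated, and a large disagreement needs most responses to be MRs. That also stands, and it is why the full range is shown.

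Fourth, every figure fixes n at 10, while 11.1 also brings eligible, evaluable Part A patients into the evaluation rule. With 12 patients, for illustration, 89.3% and 40.1% become 93.1% and 46.0%. This needs clarifying but does not remove the conflict.

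Finally, Part B response belongs to a secondary aim (Section 1.2), 11.5 describes the analyses as exploratory, and the rule neither stops accrual nor controls an error rate. This lowers the severity. It does not make two incompatible readings of a prespecified rule acceptable.

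**Conclusion.** The concern holds. Sections 11.1 and 11.2.3 conflict on whether MRs count, and no probability is given for the rule in 11.1.

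If 20% and 5% are total response rates, the rule in 11.1 is met with probability between 62.4% and 89.3%, and between 8.6% and 40.1%, depending on the MR share. The stated figures sit at the favourable end for the 20% rate and at the highest false-positive end for the 5% rate. They are the chance of meeting the rule under 11.1 only if no response is an MR. Dropping MRs from the rule is not enough by itself: the 20% and 5% must then also be read as PR/CR rates.

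These results assume 10 evaluable patients with independent outcomes and common rates, each classified as confirmed PR/CR, confirmed MR or neither. The MR shares are illustrative. This should be fixed, but it does not threaten the trial's primary aims.

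**What to change.** Before any Part B response is read, make 11.1 and 11.2.3 state the same rule. Either choice works.

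- **(a) PR/CR only.** Remove the two-MR limb and MR from the Part B response definition in 11.1, and say that 20% and 5% are PR/CR rates. The figures 89.3% and 40.1% are then the chance of meeting the rule at n = 10.
- **(b) Keep the two-MR limb.** Amend 11.2.3 to count centrally confirmed MRs. Replace 89.3% and 40.1% with the composite-rule probabilities under stated PR/CR and MR rates. Reconcile footnote 3 of Section 8.1 with the 4-week confirmation that 11.1 requires for MR, and state how MR enters best response in 12.7.1.

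Under either choice, use evaluable patients in the rule as well as in the probability sentence; the rule now refers to enrolled patients. Say whether Part A patients change the denominator of 10.

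The cost is wording and a short recalculation. The sample size need not change. Under (b) the restated probability at 20% may be less favourable than 89.3%.
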